3.2.2 Exclusion criteria

• Older adults currently suffering from Influenza, COVID-19, or any other viral illness at the time of data collection that could impair their performance will be excluded. These conditions could impair their performance, potentially affecting the reliability of the outcomes. Additionally, the presence of such illnesses could pose a health risk to other participants who use the same equipment, as well as to the researcher.

3.3 Sample size

The correlational analysis was selected for determining the sample size of this study. The main reason for that is that the diagnostic accuracy and validity testing are the primary objectives of this project. Calculating the sample size based on correlational analysis offers a robust approach

to examining the relationship between game performance and cognitive status, requiring a moderate number of participants. Thus, this study, designed with a statistical power of 0.8, an alpha level of 0.05, and a medium effect size of 0.7, requires a minimum sample size of 58 participants. Twenty-nine older adults (65 and above) who meet the diagnostic criteria for MCI, and 29 older adults with typical cognition will be eligible to participate in the study. Other reasons for justifying the sample size include: 1) The statistical analyses to answer questions that aim to compare two conditions, or two groups requires a smaller sample size; and this small sample size is insufficient to justify correlational analysis. 2) the "Events Per Variable" (EPV) rule is often used in statistical modeling, particularly in logistic regression, to determine the minimum sample size needed to ensure reliable and valid results. The general rule is to have at least 10 events (outcomes of interest) for each predictor variable (151). Therefore, using regression analysis to explore the six associated factors (game performance, age, sex, educational level, tech savviness, and living status) with the presence of MCI would necessitate 60 events (instances of the outcome of interest). Assuming an equal distribution of events and non-events, at least 120 participants would be needed in total to achieve 60 events, ensuring that each predictor variable is adequately supported by the data and enhancing the reliability of the statistical model. However, for a feasibility study involving a brand-new, untested test, it is not ethical to recruit a large sample size and burden vulnerable older adults with participation. Besides, at this point of the study, it is not known how many independent variables will be included in the model and that depends on the results of the factorial analysis that precedes the logistic model. Therefore, I aim to treat the research about the associated factors with the presence of MCI (RQ4) as a pilot to gather preliminary data. This approach can help refine the research design and hypotheses, and the results can be used to justify the need for a larger study

in the future. Additionally, based on the data, a simpler model with only the strongest predictors will be used to produce a more reliable regression model. Thus, for an initial study on a new test, correlational analysis is the most practical choice, allowing us to assess concurrent validity without requiring an excessively large sample size.

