2.3.5 Serious Computer Games as screening tools for MCI

Only a handful of studies have applied SCGs for MCI screening, revealing significant differences in game performance between older adults with MCI and their healthy counterparts For instance, Zygouris et al. noted that individuals with MCI took significantly longer to complete games than their healthy counterparts (t = 4.84, p < 0.001) (139). Similarly, Gielis et al. observed distinct differences in 12 out of 23 digital biomarkers, including time-based, errorbased, and result-based metrics, highlighting substantial discrepancies between the two groups (140). Therefore, the SCGs could differentiate or classify older adults with and without MCI. However, more studies are needed to test more game scenarios and investigate the association of demographic factors with game performance in PwMCI and healthy counterparts. Research has also explored the criterion validity of the game-based screenings for MCI detection, highlighting significant correlations between game metrics and cognitive status (39,41,139–146). Numerous game metrics, including completion ability, gameplay duration, accuracy of actions, and total score, have been examined for their relationship with cognitive status. For instance, Zygouris et al. found a negative correlation (r= -0.2) between game playtime and cognitive test scores, suggesting that older adults with lower cognitive status required more time to complete games (139). Zygouris et al. also found correlations between education (r= -0.3 and r = -0.23) and age (r = 0.2 and r = 0.24) with the total time needed to complete the game (22,139). It means that a higher education level is associated with faster game completion, while older age correlates with longer completion times. Cabinio et al. found a correlation between game performance accuracy, reaction time, total playing score and cognitive status in PwMCI and the comparison group (43). Although these findings affirm the criterion validity of gamebased screenings, the correlations are not strong. Only one study explored the correlation of the

demographic variables and the game performance. Further research is necessary to clarify the relationships between traditional cognitive screening scores and various game metrics, evaluating the validity of game-based screenings.

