2.3.6 Summary and gaps

In conclusion, various studies have applied SCGs for MCI screening among older adults, revealing significant differences in game performance between those with MCI and their healthy counterparts However, despite these promising findings, several gaps and areas for further study remain evident. Notably, the correlations between the game metrics and the traditional cognitive scores found were not robust, and demographic variables were often overlooked in these analyses, limiting the concurrent validity of the used game-based screenings. This oversight

suggests a need for more comprehensive research to understand better how demographic factors might influence the outcomes of game-based cognitive screenings.

The variability in game scenarios, dependence of the results and usability on the specific games and their availability, and small sample sizes also limit the generalizability of these findings, highlighting a clear need for further research. Future studies should also focus on integrating demographic variables, employing larger sample sizes, and exploring a wider variety of game types to enhance validity and usefulness of SCGs. Furthermore, the availability of SCGs used in previous studies is limited, and they are not accessible for older adults and clinicians to use in everyday life or clinical settings.

Research should also examine the psychological impact of game-based screenings, such as state anxiety, compared to traditional screenings. Understanding the levels of anxiety induced by different types of screenings can help improve the design and implementation of SCGs, making them more user-friendly and less intimidating for older adults. This could broaden the acceptance and effectiveness of these innovative tools in MCI screening.

Moreover, there is a need to explore the integration of real-life scenarios into SCGs, such as Activities of Daily Living (ADL) and instrumental ADL (iADL), to provide a more realistic assessment of cognitive abilities. Custom-designed games that mimic real-life activities have shown promising results, and further research in this area could enhance the ecological validity of SCGs.

In conclusion, while SCGs hold great promise for MCI screening, addressing these gaps through comprehensive research will be essential for establishing their reliability, validity, generalizability and widespread applicability.

3. Method

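### Section 3.3 states 0.8 power for an effect of 0.7 whose metric, sidedness and source are not given; read as a correlation it does not lead to 58, and it is not reconciled with the weak correlations in the protocol's own review

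*Protocol*

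**What the plan says.** Section 3.3 chooses correlational analysis as the basis for the sample size, because diagnostic accuracy and validity are the primary objectives. It describes the study as "designed with a statistical power of 0.8, an alpha level of 0.05, and a medium effect size of 0.7" and concludes that it "requires a minimum sample size of 58 participants", split into 29 with MCI and 29 with typical cognition. No source is given for 0.7.

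The literature review bears on the same quantity. Section 2.3.5 reports that an earlier virtual-supermarket study "found a negative correlation (r= -0.2) between game playtime and cognitive test scores", and comments on the body of such findings that "the correlations are not strong". Section 2.3.6 repeats that "the correlations between the game metrics and the traditional cognitive scores found were not robust".

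Section 1.3 asks RQ2 about people with typical cognition and people with MCI, without saying whether the two groups are pooled. Section 3.9 plans correlations of the game metrics with MoCA and Qmci totals and sub-scores. It judges concurrent validity by how near the coefficient comes to one. It attaches an alpha level to RQ1 and RQ5, but not to RQ2.

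**The concern.** A power statement tells the reader what the study can detect. This one cannot be used that way. The effect has no metric, so the claim cannot be checked as written. On the most natural reading, a correlation of 0.7, it does not produce 58. The planning value is also far from the only comparable coefficient the protocol quotes, and nothing explains why G3 should do so much better than earlier games.

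RQ2 is the question that set the sample size. A reader who takes the 0.8 at face value will think the study is well placed to measure concurrent validity whatever the true correlation. In fact its precision is adequate for moderate correlations and poor for weak ones.

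**Working it through.** **Inputs.** Power 0.8, alpha 0.05, effect 0.7, N = 58 as 29 + 29 (Section 3.3); r = -0.2 (Section 2.3.5). Sidedness is not stated, so two-sided is assumed and one-sided is also shown.

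**Step 1: try to reproduce 58.** For one Pearson correlation by Fisher's z, n = ((z_alpha + z_power) / atanh(r))² + 3.

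- r = 0.7, two-sided: (2.80 / 0.867)² + 3 = 13.4, so 14. One-sided: 12. Applied in each group, two-sided: 28 in total.
- Power at n = 58 and r = 0.7: atanh(0.7) × √55 = 6.43, far above 1.96, so power is near 1.
- Read instead as a standardised difference between two means, 0.7 needs 33 to 34 per group two-sided (66 to 68 in total), and 29 per group gives 75 to 76% power. One-sided it needs 26 per group (52).
- A few routes do land on or near 29 per group: a one-sided comparison of two independent correlations with a Fisher-z difference of 0.7 (28.2, so 29), or a one-sided mean difference of 0.7 with an unstated 10% dropout allowance (26 / 0.9 = 28.9, so 29). Neither is the analysis Section 3.3 describes.

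The stated figure is therefore not reproduced from the stated inputs.

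**Step 2: what 58 does deliver.** Smallest |r| with 80% power, two-sided:

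- Pooled, n = 58: tanh(2.80 / √55) = 0.36.
- Within a group, n = 29: tanh(2.80 / √26) = 0.50.

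Power at n = 58, two-sided, is approximately Phi(atanh(r) × √55 − 1.96):

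| True \|r\| | atanh(r) × √55 | Power |
|---|---|---|
| 0.20 | 1.50 | 32% |
| 0.30 | 2.30 | 63% |
| 0.36 | 2.80 | 80% |
| 0.50 | 4.07 | 98% |

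Other methods agree. At 0.2, simulation of the t-test on r gives 32.7% and the noncentral t 33.3%; at 0.3, simulation gives 64%. One-sided power at 0.2 is 44 to 46%. Within a group of 29, two-sided power at 0.2 is about 18%. For 80% power at 0.2, n would be 194 two-sided or 154 one-sided.

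**Step 3: precision.** For an observed r = 0.2 at n = 58, atanh(0.2) = 0.203 and 1.96 / √55 = 0.264. The interval on the z scale is -0.062 to 0.467, which back-transforms to a 95% CI of about -0.06 to 0.44.

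**The case against.** Four points on the other side deserve weight.

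- **The 0.8 is conditional on 0.7.** A reader might infer from the 33% that the stated power is simply false. The documents do not support that. Low power at a different effect shows that 0.7 lacks justification, not that power at 0.7 is below 0.8; if 0.7 is a correlation, power there is near 1. This stands.
- **The -0.2 is a thin anchor.** It is one metric, playing time, in one study of another game, while Section 3.6 lists six G3 metrics. The same study is quoted with t = 4.84 for completion time between groups. Its size is not in the documents; assuming 30, 50 or 150 degrees of freedom, t / √(t² + df) gives 0.66, 0.56 or 0.37. That is a group contrast rather than a correlation with a test score, so it does not show that RQ2 is well powered. It does mean that 0.2 cannot be taken as the expected value for G3. This stands.
- **RQ2 has no significance rule.** A reader might infer that a real association would be missed two times in three, or that a null result would be taken as a lack of validity. Section 3.9 says neither; it reads RQ2 by the size of the coefficient. Those consequences are not in the text.
- **0.7 might be a target, and this is a feasibility study.** It could be the correlation worth having rather than the one expected, but Section 3.3 calls it only a medium effect size. The feasibility framing supports keeping 58 people. It does not supply a basis for the power figure, and Section 3.3 designates only RQ4 as a pilot.

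**Conclusion.** The power sentence in Section 3.3 should not stand. Its effect size has no metric, sidedness or source. As a correlation it implies about 14 participants rather than 58, and it is not reconciled with a review that quotes -0.2 and calls such correlations weak. What 58 people support at two-sided alpha 0.05 is 80% power for |r| of about 0.36 pooled, or about 0.50 within a group of 29, with power of about 33% at 0.2.

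These figures assume one Pearson test at a time on approximately bivariate normal data. The 33% further assumes that G3 resembles the one quoted coefficient, which is why a range is needed. The finding concerns a planning figure and its justification. It does not show that RQ2 will fail, or that 58 is the wrong number for a feasibility study.

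**What to change.** Keep N at 58.

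- **Section 3.3:** replace the power sentence with what 58 delivers for a Pearson correlation at two-sided alpha 0.05: 80% power for |r| of about 0.36 pooled (about 0.50 within a group of 29), with power of about 33% at 0.2, 64% at 0.3, 80% at 0.36 and 98% at 0.5. If a one-sided test is intended, say so; power at 0.2 is then about 45%. Name the effect metric, the sidedness and whether RQ2 is analysed pooled or within group. If 0.7 is kept as a target for good validity, label it as that.
- **Section 3.9:** report each RQ2 correlation with its 95% confidence interval and interpret the interval. Do not use 0.36 as a cut-off for validity or for calling a result inconclusive; it is a by-product of N.

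The cost is wording in two sections and a less favourable stated power. No extra participants are needed.

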3.2 Participants

3.2.1 Inclusion criteria

- Older adults who are aged 65 and above with typical cognition or MCI as reported by themselves, or a health care professional.
- Older adults participating in this study must have MoCA score of 18 or higher.
- Older adults participating in the study must have functional vision and hearing, with or without aids such as glasses or hearing aids that enable them to interact with the game and comprehend the instructions. As part of the study recruitment activities, the researcher will explain the tasks required and discuss the vision and hearing demands.

- Older adults participating in the study must be capable of communicating and comprehending assessments, instructions, and simple sentences in English, as communication and comprehension is essential for interacting effectively with game components and the researcher. To assess their communication, reading, and comprehension skills, the researcher will provide participants with a few sentences in English related to the game content. Participants will be asked to read these sentences aloud and explain the meaning of the sentence to confirm their ability to read and understand the content.
- Older adults participating in the study must have adequate upper extremity function to play the game, using a mouse and do paper-and-pencil based measurements, using a pencil. During the study's introduction and training part of the game, potential participants can report any physical limitations. The researcher will also screen for these issues.

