3.6 Variables

The study variables are the following:

- Game performance collected through various game metrics, including total time of
 playing, the ability to complete the whole game, the ability to manage the budget, number
 of errors, the number of checking the shopping list, and the game performance accuracy.
 - Total Time of playing: This numerical variable refers to the total time that takes to complete all 6 stages in seconds with the maximum of 1800 seconds.
 - The ability to complete the game: This binary variable (1= Could complete, 0= Could not complete) refers to the participant's ability to complete all the 6 stages of the game.
 - The ability to manage the budget: This binary variable (1 = Could manage, 0 =
 Could not manage) refers to the participant's ability to keep their purchases equal to or below the budget limit provided for each level.
 - The number of errors: This numerical variable refers to the total number of mistakes made by participants, including mistaken, missed, and repeated items purchased.
 - The number of times the participant opens up the reading list: This numerical variable refers to the total number of times the participant open and check the shopping list within the 6 stages.
 - O The game accuracy: This numerical variable represents the success in the game, ranging from 0 to 100, where higher values mean higher game performance.

Demographics

 Age (In number of years): It refers to the chronological age of an individual in years at the time of data collection. This variable is considered as numerical in this study.

- Sex at birth: It refers to sex assigned at birth. Categories for this variable are male and female.
- Level of education: It refers to the highest degree or level of school completed by the participants. Categories for this variable are elementary school, high school, bachelor's degree, master's degree, and higher.
- Technology savvy: This categorical refers to the familiarity and experience of the
 participants with technology. It will be collected and measured based on the
 number of technological devices they use and the frequency of their usage.
- Living status: It refers to the participants' living condition. Categories for this
 variable are living alone, living with family, and living in an institution

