3.9 Data analysis

To explore the difference between game performance in PwMCI and healthy comparison group (RQ1), the Unpaired t-test or Mann-Whitney U test as appropriate (155), with an α level of 0.05, will be applied. If the mean difference is statistically significant, it indicates that G3 can classified older adults with typical cognition and older adults with MCI based on their game performance. In addition, a two-way factorial multiple analysis of covariance (MANCOVA) (155) will be performed to compare the effects of demographics as covariates on the differences between groups.

To explore the association between the game performance and traditional cognitive tests, including MoCA and Qmci (RQ2), correlational analysis (155) between the game metrics and the scores of each traditional cognitive tests, including total score sub-scores such as memory and executive functions will be conducted. If the correlation coefficient (r) is positive closer to one, it means that the concurrent validity of G3 as an MCI screening tool is good.

To investigate the diagnostic accuracy of the game-based screening (RQ3), formulas will be used as follows:

Sensitivity: Proportion of true positives correctly identified = $\frac{TP}{TP+FN}$

Specificity: Proportion of true negatives correctly identified = $\frac{TN}{TN+FP}$

Accuracy: Overall correctness of the testx = $\frac{\text{TP+TN}}{\text{Total Population}}$

Where TP: True Positives, TN: True Negatives, FN: False Negatives, FP: False Positives (155). Additionally, the interpretation of the Receiver Operating Characteristic (ROC) and Area Under the Curve (AUC) will be used for examination of diagnostic accuracy (155). The ROC curve is a graphical plot that illustrates the diagnostic ability of a binary classifier system as its discrimination threshold is varied. The curve is created by plotting the True Positive Rate (TPR) against the False Positive Rate (FPR) at various threshold settings (155).

The following steps will be used to calculate the ROC curve:

Firstly, the True Positive Rate (TPR), also known as sensitivity or recall, will be determined using the formula:

$$TPR = \frac{TP}{TP + FN}$$

Secondly, the False Positive Rate (FPR), also known as (1 - specificity), will be determined using the formula:

$$FPR = \frac{FP}{FP+TN}$$

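### The sample size of 58 does not follow from the stated correlational inputs: a correlation of 0.7 tested against zero needs 11 to 14 participants

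*Protocol*

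**What the plan says.** Protocol section 3.3 opens with the basis of the calculation: "The correlational analysis was selected for determining the sample size of this study". It then describes the study as "designed with a statistical power of 0.8", and continues that "an alpha level of 0.05, and a medium effect size of 0.7, requires a minimum sample size of 58 participants", split into 29 people with MCI and 29 with typical cognition. It does not name the effect-size metric, the null value, the sidedness or the test.

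Section 3.9 says how research question 2 will be answered: "correlational analysis (155) between the game metrics and the scores of each traditional cognitive tests", covering total scores and sub-scores, with a coefficient closer to one read as better concurrent validity. It plans no test that compares correlations between the two groups, and no test against a null value other than zero.

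The same part of section 3.3 says that the events-per-variable rule for the logistic model would call for 120 participants, and treats that analysis as a pilot. The correlational calculation is therefore the only one offered in support of 58.

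**The concern.** A correlation of 0.7 is strong, and detecting one with 80% power takes few participants. A requirement of 58 looks far too large for that target. The phrase "a medium effect size of 0.7" adds to the doubt, because without a metric it could mean a correlation, a standardised mean difference or something else, and these lead to different sample sizes.

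What is at stake is the reader's understanding of what the study was sized to detect. The text presents 58 as the minimum for an effect of 0.7. If 58 really corresponds to a much smaller correlation, or to a different test, that statement misinforms anyone judging the design or the burden on participants. Enrolment itself is not threatened, because 58 exceeds what a correlation of 0.7 needs.

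**Working it through.** **Inputs.** Power 0.8, alpha 0.05, effect size 0.7 and total 58 as 29 + 29 (section 3.3); the planned analysis is a correlation of a game metric with a test score (section 3.9). Sidedness is not stated, so both are tried. The effect is read first as a correlation r, because the stated basis is correlational.

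**1. One correlation against zero, Fisher z.** n = ((z_alpha + z_beta) / atanh(r))² + 3, with z_beta = 0.842 and atanh(0.7) = 0.867.

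- Two-sided: ((1.960 + 0.842) / 0.867)² + 3 = 13.43, so 14.
- One-sided: ((1.645 + 0.842) / 0.867)² + 3 = 11.22, so 12.

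The plan's 58 is not reproduced.

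**2. The same test, exact bivariate normal.** Two-sided n = 13 (power 0.817; 0.778 at n = 12). One-sided n = 11 (power 0.833; 0.793 at n = 10).

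**3. Run in each group separately.** 2 × 11 = 22 up to 2 × 14 = 28 in total, still not 58.

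**4. Power at r = 0.7, two-sided.** Power is approximately Φ(atanh(0.7) × √(n − 3) − 1.960).

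- n = 58: 0.999996 (exact 0.999995).
- n = 29: 0.9931 (exact 0.9940).

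**5. Correlation detectable with 80% power, two-sided.** r = tanh(2.802 / √(n − 3)).

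- n = 58: tanh(2.802 / √55) = 0.361 (exact 0.358).
- n = 29: tanh(2.802 / √26) = 0.500 (exact 0.493).

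**6. Routes that do reach 29 per group or 58 in total.**

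| Route | Result | What it adds or changes |
|---|---|---|
| Two independent correlations, Cohen's q = 0.7, one-sided: 2 × (2.487 / 0.7)² + 3 | 28.23, so 29 per group | Effect metric q, one-sided test, and a between-group comparison |
| r = 0.7 against a null of 0.3, two-sided | 28.23, so 29 | A non-zero null |
| r = 0.50 against zero, two-sided, exact | 29 (power 0.814; 0.799 at 28) | Effect 0.50 in place of 0.7 |
| r = 0.36 against zero, two-sided, exact | 58 (power 0.805; 0.798 at 57) | Effect 0.36 in place of 0.7 |

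With q = 0.7 two-sided, the first route gives 2 × (2.802 / 0.7)² + 3 = 35.04, so 36 per group and 72 in total.

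**7. Reading 0.7 as a standardised mean difference.** A two-sample t-test needs 34 per group (68) two-sided or 26 per group (52) one-sided. Neither is 58. Section 3.3 also says that comparisons of two groups need fewer participants than the correlational analysis. At 0.7 on both scales, two-sided, the opposite holds for the unpaired t-test: 68 against 14.

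**The case against.** The best defence is the first route in the table. If 0.7 is Cohen's q for comparing two independent correlations, tested one-sided, then power 0.8 and alpha 0.05 give exactly 29 + 29 = 58, and the two-group split fits. Section 3.3 never says that 0.7 is r, so 58 should not be called impossible. That stands. But the reading needs an unstated metric and an unstated one-sided test, and it powers a comparison that section 3.9 does not plan. If 58 came from there, the calculation answers a different question from research question 2.

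A second objection is that setting a two-group total against a single-sample n exaggerates the gap, since research question 2 can be read as asking for correlations within each group. This is fair. Pooled, the ratio runs from 58/14 = 4.1 to 58/11 = 5.3. Within groups, it runs from 29/14 = 2.1 to 29/11 = 2.6. The mismatch remains on either reading.

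Third, the consequence is small. The protocol also argues for a modest sample from feasibility and participant burden, and section 3.11 lists sample size as a limitation. That limits the importance of the point but does not make the stated calculation correct.

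Finally, a detectable correlation computed at n = 58 assumes bivariate normality, which is doubtful when two groups recruited by cognitive status are pooled. This is a fair caution about the replacement figure, which must carry its assumptions.

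A statistical analysis plan could not settle the matter by supplying detail, because the protocol itself states both the inputs and the result.

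**Conclusion.** The concern holds. For the type of correlation the protocol plans, the stated inputs require 11 to 14 participants, or 22 to 28 if the test is run in both groups. They do not require 58. Every route found to 29 per group or 58 in total adds or changes an input, and these routes disagree about what is being tested, so a reader cannot recover the intended one. The justification is either wrong as written or untraceable.

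Two-sided with 80% power, 58 participants detect a correlation of about 0.36, and one group of 29 detects about 0.50. These figures assume one Pearson correlation tested against zero, bivariate normality, complete data and no adjustment for multiple testing. No shortage of participants for research question 2 is shown. The defect lies in the stated justification, and it should be corrected.

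**What to change.** Keep 58. In section 3.3, replace the sentence that derives it with one of two texts.

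- State the test, effect metric, null value and sidedness that actually give 58, and make them match the analysis planned for research question 2.
- Or state what 58 delivers, as a sensitivity statement: *For a single Pearson correlation between one numerical game metric and one total test score, tested against zero with two-sided alpha 0.05 and 80% power, and assuming bivariate normality, complete data and no multiplicity adjustment, 58 participants detect an absolute correlation of about 0.36, or about 0.50 within one group of 29.*

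With the second text, add three cautions. The figure does not carry over directly to the binary metrics in section 3.6 (completing the game, managing the budget). The entry rule in section 3.2.1, "Older adults participating in this study must have MoCA score of 18 or higher", restricts the range of scores. Pooling two groups recruited by cognitive status makes bivariate normality an approximation.

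The cost is wording only, with no change to enrolment, conduct or analysis.

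### Section 3.3 gives no support for its claim that two-group comparisons need fewer people: on a two-sided reading with d = 0.7, RQ1 would need 68, not 58

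*Protocol*

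**What the plan says.** Section 3.3 takes its sample size from one analysis: "The correlational analysis was selected for determining the sample size of this study". The study is "designed with a statistical power of 0.8, an alpha level of 0.05, and a medium effect size of 0.7" and so "requires a minimum sample size of 58 participants". These are split as "Twenty-nine older adults (65 and above) who meet the diagnostic criteria for MCI, and 29 older adults with typical cognition".

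The section then lists other reasons for the figure. The first is that "The statistical analyses to answer questions that aim to compare two conditions, or two groups requires a smaller sample size", and that such a smaller sample would not be enough for the correlation. No effect size, number or power is given for any two-group or two-condition comparison.

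Section 3.9 gives RQ1 (game performance, MCI versus typical cognition) "the Unpaired t-test or Mann-Whitney U test as appropriate (155), with an α level of 0.05". It gives RQ5 (state anxiety, game versus traditional tests) a paired t-test or Wilcoxon signed-ranks test. Neither section states whether tests are one- or two-sided. RQ1 as worded in Section 1.3 asks whether the groups differ at all, which suggests two-sided.

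**The concern.** The statement covers two kinds of comparison with different needs. A paired comparison of two conditions is economical because each person serves as his or her own control. A comparison of two independent groups is not, and at moderate standardized differences it can need more than 58 people.

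The statement stands among the reasons that justify 58, so it reassures the reader that the group comparison is no constraint. The same section treats the logistic regression (RQ4) quite differently: it says openly that the sample falls short and calls that analysis a pilot. Section 3.9 takes a significant RQ1 result to show that the game can classify the two groups. If RQ1 has less than the conventional power, a real difference could be missed, and nothing in the sample size section warns of that.

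**Working it through.** **Inputs from the protocol.** Power 0.80, alpha 0.05, effect size 0.7 (metric not named, attached to the correlational analysis), total 58, allocation 29:29 (all Section 3.3). RQ1 test: unpaired t-test or Mann-Whitney; RQ5 test: paired (Section 3.9).

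**Assumptions.** Sidedness is not stated, so both are shown. No effect size is given for RQ1. The value 0.7 is tried as a standardized mean difference d, with 0.5 as an illustration. No dropout is assumed.

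**1. The plan's own figure.** For a single correlation, N = ((z_alpha + z_power) / atanh(r))² + 3.

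- r = 0.7, two-sided: ((1.960 + 0.842) / 0.867)² + 3 = 13.4, so 14. One-sided: 11.2, so 12.
- So 58 is not what a correlation of 0.7 requires. Solving backwards, N = 58 corresponds to r of about 0.36 two-sided or 0.32 one-sided.
- Two unstated readings do give 29 per group: a one-sided comparison of two independent correlations with Cohen's q = 0.7 (28.2 per group), and r = 0.5 two-sided within each group (29.0).

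The metric of 0.7 therefore cannot be recovered from the text, and what follows has to be conditional.

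**2. RQ1, independent groups.** By the normal approximation, n per group = 2 × ((z_alpha + z_power) / d)². For d = 0.7 two-sided this is 2 × (2.802 / 0.7)² = 32.04, so 33. The t-test itself (noncentral t) needs 33.02, so 34.

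| d | Sides | n per group (t-test) | Total | Power at 29 per group (t-test) |
|---|---|---|---|---|
| 0.7 | two | 33.02 → 34 | 68 | 74.5% |
| 0.7 | one | 25.94 → 26 | 52 | 83.8% |
| 0.5 | two | 63.77 → 64 | 128 | 46.5% |
| 0.5 | one | 50.15 → 51 | 102 | 59.3% |

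For the Mann-Whitney test at d = 0.7 with normal data:

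- Two-sided power at 29 per group is 71.5% by simulation (40,000 runs), or 72.5% from the efficiency factor 3/π. The number needed is 33.02 / 0.955 = 34.6, so 35 per group (70 in total).
- One-sided power is about 82%.

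The smallest difference detectable with 80% power at 29 per group is d = 0.75 two-sided, or 0.66 one-sided.

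**3. RQ5, paired.** At a standardized paired difference of 0.7, the paired t-test needs 18.03 people two-sided, so 19. The statement is right for this half at that value.

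**4. Is a group comparison cheaper in general?** Put both analyses on one scale with r = d / √(d² + 4). For d = 0.7, r = 0.7 / √4.49 = 0.330. Two-sided, before rounding:

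| r | Equivalent d | N, correlation | N, two groups (total) |
|---|---|---|---|
| 0.30 | 0.63 | 84.9 | 81.3 |
| 0.33 | 0.70 | 69.6 | 66.0 |
| 0.36 | 0.77 | 58.3 | 54.7 |
| 0.50 | 1.15 | 29.0 | 25.6 |
| 0.70 | 1.96 | 13.4 | 10.5 |

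The two needs differ by three or four people throughout. Part of that gap comes from the approximations and much of it goes in rounding to whole groups (70 versus 68 at r = 0.33). The group comparison is about equal, or very slightly cheaper.

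**The case against.** The strongest reply is that the calculation borrows a number. Section 3.3 gives 0.7 for the correlational analysis and never calls it a standardized mean difference or assigns it to RQ1. If 0.7 is a correlation, the matched d is 1.96 and about six people per group suffice. If the RQ1 test is one-sided, d = 0.7 needs 52, which is below 58. On a matched scale the statement is even marginally true: at r = 0.36, the correlation that 58 supports two-sided, the group comparison needs 28 per group, or 56. All of this stands, and it rules out calling the statement simply false.

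A reader might also infer that the protocol promises 80% power for RQ1. It does not; it says why the group comparison did not set the sample size. Nor does it say that a null RQ1 result means no difference, since Section 3.9 interprets only a significant one. RQ1 is listed first, but Section 3.3 names diagnostic accuracy and validity as the primary objectives, and Section 3.11 concedes that the sample should be larger.

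Finally, Section 3.9 calls an AUC of 0.7 to 0.8 acceptable. Under equal-variance normality, d = √2 × Φ⁻¹(AUC), so an AUC of 0.70 is d = 0.74, with 79% power at 29 per group, and 0.75 is d = 0.95, with 95%. RQ1 is thus close to or above 80% power wherever the game discriminates acceptably by the protocol's own scale. That limits the harm.

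None of this supplies the missing basis. The one-sided rescue is narrow: at d = 0.5 it still needs 102. The wording of RQ1 points to a two-sided test. A matched difference of 1.96 SD is one the protocol nowhere asserts. The matched-scale result shows near-equality, not a saving that could serve as a reason for 58.

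**Conclusion.** The claim about two-group comparisons is unsupported as written, and it is wrong on one natural reading. With d = 0.7 and a two-sided 5% test, RQ1 needs 68 rather than 58, and 29 per group gives about 75% power by t-test or 71–72% by Mann-Whitney. One-sided at the same d it would be right (52 needed, about 84% power by t-test). For the paired RQ5 comparison it is reasonable.

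The documents do not support the stronger reading that independent-group comparisons are always the more demanding analysis, or that RQ1 fails a stated power target. The shortfall is modest, and it rests on two things the protocol leaves open: the metric of 0.7 and the sidedness of the test. That 58 does not follow from a correlation of 0.7 is a separate and larger problem in the same section, and settling it would also settle the metric here.

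**What to change.** In Section 3.3, limit the statement about smaller samples to the paired comparison (RQ5), and state the metric and sidedness of the 0.7. Then add, for RQ1:

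> With 29 per group, RQ1 has 80% power for a standardized difference of about 0.75 or more (t-test, two-sided 0.05), and about 75% at 0.7. A non-significant RQ1 result will be interpreted from its confidence interval, not as absence of a difference.

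If a one-sided test is intended, say so and give the matching figure (a detectable difference of about 0.66). The cost is a few sentences and no extra participants. The stated position for RQ1 becomes slightly less favourable.
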